- (b) venetoclax dosing and lab monitoring is per label. Tumor lysis syndrome monitoring as per Appendix D and E, which includes additional chemistry monitoring, potential IV fluid administration, and potential inpatient hospitalization if clinically indicated and in accordance with venetoclax standard of care.
- (c) CMP includes the following: Na, K, Chloride, Bicarbonate, BUN, creatinine, glucose; calcium; total protein, albumin, AST, ALT, total bilirubin, alkaline phosphatase
- (d) For patients with high tumor burden OR median tumor burden AND creatinine clearance <80ml/min, TLS monitoring will be done according to US Prescribing Information, i.e. In hospital: For first dose of 20mg and 50 mg: Predose,4, 8, 12 and 24 hours; Outpatient: For subsequent ramp-up doses: Predose,6 to 8 hours, 24 hours. For patients with low tumor burden or medium tumor burden wuth creatinine clearance 80ml/min or greater, assessments will be done outpatient, and the day 16, 23, and 30 visits are not required.
- (e) Venetoclax is dispensed AFTER CBC diff, CMP, phos, uric acid, and LDH results are reviewed by PI, subI, or study team.

Cycle	Cycle 2	Cycle 3	Cycle 4	Cycle 5	Cycle 6
Day (a)	1	1	1	1	1
MD Visit	x	x	x	x	x
Vitals signs	х	x	x	х	х
CBC diff	x	х	x	x	x
CMP (b)	x	x	x	x	x
Phos	x	x	x	x	x
Uric acid	x	x	x	x	х
LDH					
Correlative Lab Draw					
D	500 / 0	500 / 0	500 / 0	500 / 0	F00 / 0
Rituximab	500 mg/m2	500 mg/m2	500 mg/m2	500 mg/m2	500 mg/m2
		400 v 1 ath	400 v 1	400 1	400 v 1
Vanataslay (IDS)	400 mg v 1 month sumply		400 mg x 1 month	400 mg x 1 month	400 mg x 1 month
Venetoclax (IDS)	400 mg x 1 month supply	supply	supply	supply	supply
	NOTES		 		
	(a) Protocol allowed date v	windows for Cycles 2	-22 are - 14 days or	+ 14 days	
	1` '		•	· ·	-1-:
	(b) CMP includes the follow			creatinine, giucose; c	calcium; total
I	protein, albumin, AST, ALT	, totai bilirubin, alkal	ine phosphatase		

Cycle	Cycle 7	Cycle 10	Cycle 13	Cyle 16	Cycle 19	Cycle 22	End of Study
Cyole	Cycle 7	Cycle 10	Cycle 15	Cylic 10	Cycle 13	Cycle 22	C24D28 +/- 14
Day (a)	1	1	1	1	1	1	days
MD Visit	x	×	×	×	x	x	x
Vitals signs	x	x	×	×	×	x	x
_							
CBC diff	x	x	×	x	×	x	x
CMP (b)	x	x	×	x	x	x	x
Phos	x	x	x	x	x	x	
Uric acid	x	x	x	x	x	x	
LDH							
Correlative Lab Draw							x
	400 mg x 3 month	-		400 mg x 3 month		-	
Venetoclax (IDS)	supply	supply	supply	supply	supply	supply	
Ct or MRI thorax (c)		x{d}					x (d)
CT or MRI abdomen/pelvis (c)		x{d}					x (d)
Marrow biopsy and aspirate procedure		x{e}					x {e }

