- Tumor lysis syndrome monitoring as per Appendix D and E, which includes additional chemistry monitoring, potential IV fluid administration, and potential inpatient hospitalization if clinically indicated and in accordance with venetoclax standard of care.

(Only required if High Tumor Burden prior to venetoclax initiation): On Day 16 of Cycle 1, the following are completed:

- Laboratory examinations: CBC w/differential, comprehensive metabolic panel, phosphorous, uric acid, LDH
- 2nd dose of venetoclax 100 mg PO after labs are resulted and reviewed by treating physician or investigator.
- Patients continue venetoclax 100 mg PO daily C1D16 C1D21.

On Day 22 of Cycle 1, the following are completed:

- Current medications will be recorded in the subject's medical record.
- Laboratory examinations: CBC w/differential, comprehensive metabolic panel, phosphorous, uric acid, LDH
- Dispensing and initial dose of Venetoclax 200 mg PO dose level. (7 day supply).
- Tumor lysis syndrome monitoring as per Appendix D and E, which includes additional chemistry monitoring, potential IV fluid administration, and potential inpatient hospitalization if clinically indicated and in accordance with venetoclax standard of care.

(Only required is High Tumor Burden prior to venetoclax initiation): On Day 23 of Cycle 1, the following are completed:

- Laboratory examinations: CBC w/differential, comprehensive metabolic panel, phosphorous, uric acid, LDH
- 2nd dose of venetoclax 200 mg PO after labs are resulted and reviewed by treating physician or investigator.
- Patients continue venetoclax 200 mg PO daily C1D23 C1D28.

On Day 29 of Cycle 1, the following are completed:

- Current medications will be recorded in the subject's medical record.
- Laboratory examinations: CBC w/differential, comprehensive metabolic panel, phosphorous, uric acid, LDH
- Dispensing and initial dose of Venetoclax 400 mg PO dose level (7 day supply).
- Tumor lysis syndrome monitoring as per Appendix D and E, which includes additional chemistry monitoring, potential IV fluid administration, and potential inpatient hospitalization if clinically indicated and in accordance with venetoclax standard of care.

(Only required is High Tumor Burden prior to venetoclax initiation): On Day 30 of Cycle 1, the following are completed:

• Laboratory examinations: CBC w/differential, comprehensive metabolic panel,

phosphorous, uric acid, LDH

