9.0 Statistical Considerations

9.1 General Considerations

This is a pilot/feasibility clinical trial, with the primary feasibility endpoint being debulking of tumor burden to meet criteria for low Tumor Burden upon the completion of cycle 0

.The primary efficacy endpoint is the percentage of patients that have a decrease in tumor burden from levels of disease that meet "Medium/High-tumor burden" criteria to "Low tumor burden" criteria for disease burden following a maximum of 2 cycles of HDMP + Rituximab (called cycle 0 in the protocol schedule of events).

Tumor burden will be assessed prior to initiation of therapy, and after each cycle of HDMP + Rituximab (maximum 2 cycles). See section 8.1 for the definition of these categories of tumor burden.

The secondary endpoints are as follows:

- Percentage of patients that have a decrease in tumor burden from levels of disease that meet "Medium/High-tumor burden" to meet "Low tumor burden" criteria for disease burden following 1 cycle of HDMP + Rituximab.
- Percentage of patients that have a decrease in tumor burden from levels of disease that meet "Medium/High-tumor burden" to meet "Low tumor burden" criteria for disease burden following 2 cycles of HDMP + Rituximab.
- Rate of laboratory TLS (from start of treatment until completion of venetoclax ramp-up).
 See Appendix B for definition and grading of TLS.
- Rate of clinical TLS (from start of treatment until completion of venetoclax ramp-up)

- Adverse events by CTCAE4 definitions and iwCLL definition for hematologic AEs (see section 10.0 for iwCLL definition of hematologic AE).
- Overall Response rate (ORR), Partial Response (PR) rate, and Complete response (CR) rate per iwCLL criteria after 9 months of venetoclax and at completion of treatment. See section 8.2 for iwCLL criteria for definitions of each level of response. ORR includes all patients who have either a PR or CR.
- Undetectable minimal residual disease (MRD) rate based on bone marrow biopsy after 9
 months of venetoclax, and at completion of treatment. Undetectable MRD is defined as
 less than 0.01% CLL cells.

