9.7.2 Secondary Analyses

Analysis for the secondary analyses will use the data combined from both the stages. Linear models, logistic models or Cox models will be used to adjust for covariates including the stage variable and whether a patient has a debulking response after the first cycle.

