Venclexta can cause rapid reduction in tumor and thus poses a risk of TLS in the 5-week rampup phase. Changes in blood chemistries consistent with TLS that require prompt management can occur as early as 6 to 8 hours following the first dose of Venclexta and at each dose increase.

The risk of TLS is a continuum based on multiple factors, including tumor burden and comorbidities. Perform tumor burden assessments, including radiographic evaluation (e.g. CT scan), assess blood chemistry (potassium, uric acid, phosphorous, calcium, and creatinine) in all patients and correct pre-existing abnormalities prior to initiation of treatment with venetoclax. Reduced renal function (creatinine clearance < 80 ml/min) further increases the risk. The risk may decrease as tumor burden decreases.

The following table describes the recommends TLS prophylaxis and monitoring during venetoclax treatment based on tumor burden determination from clinical trial data.

Tumor Burden Categories and TLS Monitoring and Risk Mitigation Recommendations

Tumor Burden Category	Tumor Burden at start of venetoclax	Prophylaxis		Blood chemistry monitoring ^{c,d}
		Hydration ^a	Anti- hyperuricemics	Setting and Frequency of Assessments
Low	All measurable LN with the largest diameter < 5 cm by radiologic assessment AND ALC < 25 × 109/L	Oral (1.5 – 2L)	Allopurinol ^b	Outpatient - Pre-dose, 6 to 8 hours, 24 hr at first dose of 20 mg and 50 mg - Pre-dose at subsequent ramp-up doses
Medium	Any measurable LN with the largest diameter ≥ 5 cm but < 10 cm by radiologic assessment OR ALC ≥ 25 × 10 ⁹ /L	Oral (1.5 – 2L) and consider additional intravenous	Allopurinol	Outpatient - Pre-dose, 6 to 8 hours, 24 hr at first dose of 20 mg and 50 mg - Pre-dose at subsequent ramp-up doses - Consider hospitalization for patients with CrCl < 80 ml/min at first dose of 20 mg and 50 mg; see below for monitoring in hospital
High	Any measurable LN with the largest diameter ≥ 10 cm by radiologic assessment OR ALC ≥ 25 × 10 ⁹ /L AND any measurable LN with the largest diameter ≥ 5 cm	Oral (1.5 – 2L) and intravenous (150 – 200 ml/hr as tolerated)	Allopurinol; consider rasburicase if baseline uric acid is elevated	In hospital at first dose of 20 mg and 50 mg - Pre-dose, 4, 8, 12 and 24 hours Outpatient at subsequent ramp-up doses - pre-dose, 6 to 8 hours, 24 hours.

ALC = absolute lymphocyte count; LN = lymph node

^aAdminister intravenous hydration for any patient who cannot tolerate oral hydration.

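### Ramp-up chemistry is scheduled by tumor burden after debulking, so laboratory TLS is unequally ascertained and any contrast by debulking response is partly confounded with sampling intensity

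*Combined protocol and SAP*

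**What the plan says.** Section 9.1 lists as a secondary endpoint the "Rate of laboratory TLS (from start of treatment until completion of venetoclax ramp-up", with Appendix B for the definition. Section 9.7.2 plans linear, logistic or Cox models for the secondary analyses, to "adjust for covariates including the stage variable and whether a patient has a debulking response after the first cycle". Section 9.2 says that safety statistics are descriptive.

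Ramp-up sampling follows the burden category at the start of venetoclax (Appendix D), that is, after HDMP + rituximab.

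- **Dense schedule** (Table 3, Cycle 1, note (d)): "For patients with high tumor burden OR median tumor burden AND creatinine clearance <80ml/min, TLS monitoring will be done according to US Prescribing Information". I read the word median as Medium. In hospital this means "For first dose of 20mg and 50 mg: Predose,4, 8, 12 and 24 hours"; as an outpatient, "For subsequent ramp-up doses: Predose,6 to 8 hours, 24 hours".
- **Sparse schedule** (Low, or Medium with CrCl of 80 mL/min or more): Appendix D gives "Pre-dose, 6 to 8 hours, 24 hr at first dose of 20 mg and 50 mg" and then a pre-dose draw only. Note (d) adds that "assessments will be done outpatient, and the day 16, 23, and 30 visits are not required".

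Two other places give different rules for the later steps. Section 6.3 has "Only required if High Tumor Burden prior to venetoclax initiation): On Day 16 of Cycle 1", and likewise for Days 23 and 30, so High patients only. Footnote d of Appendix D asks for 6-8 h and 24 h chemistry at every later step in patients at risk of TLS, a term it does not define.

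**The concern.** The result of the intervention helps to decide how hard the endpoint is looked for. A patient debulked to Low moves to the schedule with fewer post-dose draws, and fewer draws can only lower the number of laboratory TLS events detected. If first-cycle debulking response then enters a TLS model, its coefficient mixes any real effect with the difference in sampling. The overall rate is also exposed: the more patients are on the sparse schedule, the more events can go unseen. Nothing in the plan addresses this, although Section 4.1 presents the approach as a way to decrease TLS risk.

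**Working it through.** **1. The plan's own figures.** The documents give no figure for TLS ascertainment or precision. The only design figures concern the primary endpoint (10 then 17 patients, stop at 2 or fewer of 10, reject at 9 or more of 17). An exact two-stage binomial calculation gives type I error 0.0402, power 0.8008 and early stopping 0.3828, matching the stated 0.04, 80% and 38.3%. TLS does not enter that design, so none of these changes.

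**2. Post-dose draws within 24 h of each step** (Table 3 grid and note (d); Appendix D).

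| Step (nominal day) | High, or Medium with CrCl <80 | Low, or Medium with CrCl >=80 |
|---|---|---|
| 20 mg (1) | 4 | 2 |
| 50 mg (8) | 4 | 2 |
| 100 mg (15) | 2 | 0 |
| 200 mg (22) | 2 | 0 |
| 400 mg (29) | 2 | 0 |
| Total draws | 14 | 4 |
| Steps covered | 5 of 5 | 2 of 5 |

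Adding one pre-dose draw per step gives 14 + 5 = 19 against 4 + 5 = 9.

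**3. Later looks.** Every patient has chemistry on Days 22 and 29 and on Cycle 2 Day 1 (Day 36, as Cycle 1 lasts 35 days). These fall 22 - 15 = 7, 29 - 22 = 7 and 36 - 29 = 7 days after the 100, 200 and 400 mg steps. That is the edge of the 7-day Cairo-Bishop window in Appendix B; the Howard table there has no window. On the nominal calendar, both groups therefore have some chemistry within 7 days at 5 of 5 steps. The allowed visit windows (up to +14 days in Cycle 1, 14 days either way from Cycle 2) can move a draw outside the 7 days. Appendix D puts the earliest chemistry changes at 6-8 h, and Table 4 in Section 7.3.4 provides for resolution within 24-48 h. A day-7 draw can miss such an event.

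**4. Link with debulking response.** Patients who start venetoclax as Low are all on the sparse schedule. Non-responders are mixed: High is dense; Medium with CrCl >=80 is sparse; Medium with CrCl <80 is dense under note (d), but has no required Day 16, 23 or 30 visit under Section 6.3. A first-cycle non-responder who reaches Low after the optional second cycle (Section 4.1) is also sparse. The confounding is partial, but runs one way.

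**5. Possible size.** Let s be the share of laboratory TLS events arising at the last three steps and m the share of those missed without a post-dose draw. Observed rate / true rate in the sparse group = 1 - s x m. Neither input is in the documents; I assume s = 0.10 to 0.60 and m = 0.50 to 1.00.

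- Mildest: 1 - 0.10 x 0.50 = 0.95.
- Most severe: 1 - 0.60 x 1.00 = 0.40.

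With all 17 patients on the sparse schedule and an assumed true rate R of 5% to 20%, expected missed events = 17 x R x s x m. This runs from 17 x 0.05 x 0.10 x 0.50 = 0.04 to 17 x 0.20 x 0.60 x 1.00 = 2.04.

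**6. Scale.** The exact 95% interval is 0-19.5% for 0/17 and 0.1-28.7% for 1/17.

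**The case against.** The strongest reply is that little inference rests on this. There is no control arm, safety is descriptive, Section 4.3 concedes that the actual TLS rate would need a much larger study, and Section 9.7.2 does not name TLS. With 17 patients, any TLS model would be nearly uninformative whatever the sampling. All of that stands, and it limits the weight of the point. It does not remove it: TLS is a listed secondary endpoint, 9.7.2 covers the secondary analyses, and a descriptive rate can still be understated.

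Three stronger readings are tempting but not supported.

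- A reader might infer that debulked patients are examined for TLS at only 2 of 5 steps. That holds only for post-dose draws within 24 h; the day-7 chemistry is late, but it is a look.
- A reader might infer a clean split between debulked and non-debulked patients. Medium patients with CrCl >=80 whose debulking failed share the sparse schedule.
- A reader might infer a large, calculable bias. With an equal 2% risk at each step and every later event missed, detection is 1 - 0.98^5 = 9.6% against 1 - 0.98^2 = 4.0%, an apparent 59% reduction with no true effect. That sits at the extreme of the range above (three of five steps, so s close to 0.6, and m = 1). Section 2.2.3.2 puts TLS risk highest when venetoclax is started, where every patient has post-dose draws.

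**Conclusion.** The point holds as unequal ascertainment of a descriptive secondary endpoint. Post-dose chemistry within 24 h is scheduled at 5 of 5 steps (14 draws) in one group and 2 of 5 (4 draws) in the other, and membership is linked to debulking success. The overall laboratory TLS rate may be understated, and any model with debulking response as a covariate would be partly confounded with sampling, in the direction that favours debulking. The direction follows from the schedule; the size does not. The 40-95% range rests wholly on the assumed s and m.

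Clinical TLS is less exposed, because symptoms trigger a recheck under Appendix E, although Appendix B requires laboratory TLS for the clinical diagnosis. The primary endpoint, error rates and sample size are untouched. The documents do not support calling this bias in a planned treatment comparison, since none is planned.

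**What to change.** In Sections 9.1 and 9.7.2:

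1. Base any laboratory TLS comparison or model by debulking response or burden category only on draws scheduled for every patient: pre-dose, 6-8 h (the 8 h draw for inpatients) and 24 h at 20 and 50 mg; pre-dose at 100, 200 and 400 mg; and Cycle 2 Day 1.
2. Report the overall laboratory TLS rate twice, on all draws and on these common draws, each by monitoring schedule.
3. List events found only on the additional draws.

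Separately, note (d) of Table 3, Section 6.3 and footnote d of Appendix D must be reconciled on who is sampled after the later steps. I recommend no schedule; the analysis change adds and removes no draws. Reporting Cycle 0 and ramp-up TLS separately is optional.

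The cost is some SAP wording and one extra table. The downside is that events found only on the additional draws leave the comparison. The common-draw analysis also cannot recover events that nobody sampled for, so the overall rate should carry that caveat.

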- 10. Adequate renal function: Creatinine clearance based on 24 hr collection >/= 40 ml/min; OR Calculated Creatinine clearance (CrCl) ≥ 40 mL/min (based upon the Cockcroft-Gault Equation [CrCl = (140-age) * actual wt (in kg) * (0.85 if female) / (72 * Cr)].
- 11. Adequate hepatic function per local laboratory reference range as follows:
 - a. Aspartate transaminase (AST) and alanine transaminase (ALT) < 3.0X ULN
 - b. Bilirubin ≤1.5 x ULN (unless bilirubin rise is due to Gilbert's syndrome or of non-hepatic origin)

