^bStart allopurinol or xanthine oxidase inhibitor 2 to 3 days prior to initiation of VENCLEXTA. ^cEvaluate blood chemistries (potassium, uric acid, phosphorus, calcium, and creatinine); review in real time.

^dFor patients at risk of TLS, monitor blood chemistries at 6 to 8 hours and at 24 hours at each subsequent ramp-up dose.

Any subject, who at any dose level develops clinically significant electrolyte abnormalities, must have their subsequent venetoclax dose held until the electrolyte abnormalities resolve. Electrolyte changes should undergo aggressive management and further monitoring as per Appendix E (Recommendations for Initial Management of Electrolyte Abnormalities and Prevention of Tumor Lysis Syndrome [TLS]). The subject may resume dosing based on a risk assessment (including tumor burden status), as determined by the investigator. All subjects must receive the intended dose for at least 7 days before increasing to the next higher dose.

Appendix E: Recommendations for Initial Management of Electrolyte Abnormalities and Prevention of Tumor Lysis Syndrome (TLS)

Section 1: First Dose of Venetoclax on study or Dose Escalation

- Within the first 24 hours after either the first dose on study or dose escalation, if any laboratory criteria below are met, the patient should be hospitalized for monitoring and the investigator notified. No additional venetoclax doses should be administered until resolution. A rapidly rising serum potassium is a medical emergency.
- IV fluids (e.g., D5 1/2 normal saline) should be initiated at a rate of at least 1 mL/kg/hr rounded to the nearest 10 mL (target 150 to 200 mL/hr; not < 50 mL/hr). Modification of fluid rate should also be considered for individuals with specific medical needs.
- Monitor for symptoms or signs of TLS (e.g., fever, chills, tachycardia, nausea, vomiting, diarrhea, diaphoresis, hypotension, muscle aches, weakness, paresthesias, mental status changes, confusion and seizures). If any clinical features are observed, recheck potassium, phosphorus, uric acid, calcium and creatinine within 1 hour STAT.
- Vital signs should be taken at time of all blood draws or any intervention.
- The management recommendations below focus on the minimum initial responses required. If a diagnosis of TLS is established, ongoing intensive monitoring and multi-disciplinary management will be per institutional protocols.

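### Section 6.3 and Appendix D omit chemistry at 100, 200 and 400 mg that Table 3 note (d) requires for Medium burden with CrCl below 80 mL/min; TLS should also be declared descriptive

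*Combined protocol and SAP*

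**What the plan says.** Three places set the chemistry schedule for the ramp-up.

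- **Table 3, Cycle 1, note (d).** The intensive rule reads: "For patients with high tumor burden OR median tumor burden AND creatinine clearance <80ml/min, TLS monitoring will be done according to US Prescribing Information". That means in-hospital draws at 4, 8, 12 and 24 h after the first 20 mg and 50 mg doses, and outpatient draws at 6-8 h and 24 h after each later step. For Low burden, and for Medium burden with CrCl of 80 or more, "assessments will be done outpatient, and the day 16, 23, and 30 visits are not required".
- **Section 6.3.** The Day 16 block is headed "Only required if High Tumor Burden prior to venetoclax initiation", and Days 23 and 30 carry the same restriction. On Days 15, 22 and 29 the section also orders TLS monitoring by Appendices D and E for everyone.
- **Appendix D.** The Low and Medium rows give, for steps after 50 mg, "Pre-dose at subsequent ramp-up doses". For Medium burden with CrCl below 80, hospitalization is only to be considered, and only at 20 and 50 mg. Footnote d says that for "patients at risk of TLS, monitor blood chemistries at 6 to 8 hours and at 24 hours at each subsequent ramp-up dose", without defining who is at risk.

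Section 5.1 admits patients with "Calculated Creatinine clearance (CrCl) ≥ 40 mL/min", and Appendix D states: "Reduced renal function (creatinine clearance < 80 ml/min) further increases the risk".

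On analysis, 9.1 lists laboratory and clinical TLS through the end of ramp-up as secondary endpoints. Section 9.2 says safety statistics are descriptive, and 9.8 plans descriptive statistics for adverse events. Section 9.7.2 says secondary analyses may use models that adjust for stage and for debulking response after the first cycle. It does not name TLS.

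**The concern.** A Medium-burden patient with CrCl of, say, 60 mL/min falls under two different rules. Note (d) requires next-day chemistry after 100, 200 and 400 mg; 6.3 restricts those visits to High burden. This is a group the protocol itself regards as being at added risk of TLS, so the lighter reading removes safety checks where they matter.

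A second, smaller matter follows from the same schedule. Burden at the start of venetoclax decides how closely TLS is looked for, and burden after HDMP + rituximab is also the primary outcome. If the general wording of 9.7.2 were applied to TLS, an association with debulking response could partly reflect how often blood was drawn.

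**Working it through.** **1. Medium burden with CrCl below 80, place by place**

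The wording of note (d) could be parsed in two ways, but its companion sentence excuses only Low burden and Medium with CrCl of 80 or more. The intensive group is therefore High burden, plus Medium with CrCl below 80.

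| Source | 20 and 50 mg, post-dose | 100, 200 and 400 mg, post-dose |
|---|---|---|
| Table 3 note (d) | 4, 8, 12, 24 h, in hospital | 6-8 h and 24 h |
| Section 6.3 | Day 2 and Day 9 draws for all | Days 16, 23, 30 for High only; Appendices D and E on step days |
| Appendix D, Medium row | 6-8 h and 24 h; hospitalization considered | none (pre-dose only) |
| Appendix D, footnote d | not addressed | 6-8 h and 24 h if at risk of TLS (undefined) |

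Required post-dose draws within 24 h for this patient:

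- Note (d): 4 × 2 + 2 × 3 = 14, over 5 of 5 steps.
- Appendix D Medium row, outpatient: 2 × 2 + 0 × 3 = 4, over 2 of 5 steps. If hospitalized at 20 and 50 mg: 4 × 2 + 0 × 3 = 8, still over 2 of 5 steps.
- Gap at the three later steps: 2 × 3 = 6 draws, of which 3 are the next-day draws on Days 16, 23 and 30.

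**2. Coverage by schedule**

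- Intensive (High, or Medium with CrCl below 80 under note (d)): 14 draws, 5 of 5 steps.
- Light (Low, or Medium with CrCl of 80 or more): 2 × 2 + 0 × 3 = 4 draws, 2 of 5 steps.
- At 20 and 50 mg both schedules include 24 h chemistry, but with 4 draws per step against 2.

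On the light schedule, the next required draw after a later step is the next visit, nominally 7 days on. That is the edge of the 7-day Cairo-Bishop window in Appendix B. Cycle 1 visits may slip by up to 14 days, and Cycle 2 Day 1 has a window of 14 days either way. Symptomatic cases have a separate route: "If any clinical features are observed, recheck potassium, phosphorus, uric acid, calcium and creatinine within 1 hour STAT" (Appendix E). What could be missed is a transient, asymptomatic laboratory change.

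**3. Whether this separates debulked from non-debulked patients**

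Every patient at Low burden when venetoclax starts is on the light schedule. Non-debulked patients split: High, or Medium with CrCl below 80, are on the intensive schedule; Medium with CrCl of 80 or more are on the light one. Let h be the share of non-debulked patients on the intensive schedule. At h = 0 the schedules are identical and no distortion arises from them. The documents do not give h.

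For illustration, assume 10 of 17 are debulked. Patient-steps with required 24 h chemistry at 100-400 mg are then 0 of 10 × 3 = 30 in debulked patients, and between 0 (h = 0) and 21 of 7 × 3 = 21 (h = 1) in the others.

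**4. How many events there would be to analyse**

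Section 2.2.3.3 cites grade 3-4 TLS in 6 of 194 patients. Applied to 17 patients, 17 × 6/194 = 0.53 expected events, and the chance of none is (188/194)^17 = 0.59. The documents give no laboratory TLS rate. An assumed range of 5% to 20% gives 17 × 0.05 = 0.85 to 17 × 0.20 = 3.4 events, too few for a model with stage and debulking response.

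**5. The plan's own figures**

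The plan states no power or precision for TLS. The exact two-stage calculation for its Simon design (stop at 2 or fewer of 10; reject at 9 or more of 17; 30% against 60%) gives type I error 0.0402, power 0.8008 and early stopping 0.3828. These match the stated 0.04, 80% and 38.3%. Nothing here touches them.

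**The case against.** **Section 6.3 does not stand alone.** On the day of each later step it sends the site to Appendices D and E. Footnote d there asks for 6-8 h and 24 h chemistry in patients at risk of TLS, and Appendix D says CrCl below 80 raises risk. A careful site may therefore draw the samples anyway. This stands: omission is possible, not certain. But the footnote leaves its key term undefined, and the Medium row it qualifies asks only for pre-dose draws, so Appendix D does not settle the conflict.

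**A reader might infer that the trial's TLS results will be biased in favour of debulking.** The documents do not support that. No TLS comparison by debulking response is prespecified, 9.2 and 9.8 point to description, and non-debulked Medium patients with CrCl of 80 or more share the light schedule. Any numerical estimate of bias would need the distribution of TLS risk across dose steps and the chance of later detection, neither of which is given.

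**A reader might also infer that risk-adapted monitoring is itself a flaw.** It is not. The protocol adopts it from the prescribing information, the TLS objective concerns the rate under this strategy, and excused patients need no extra draws.

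**Event timing is already captured.** Onset dates are recorded (10.0) and all adverse events are listed (9.8), so a handful of events could be assigned to dose steps without a new rule. That is fair; the gain from a planned table is modest.

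**Conclusion.** The contradiction is established from the text. For Medium burden with CrCl below 80, note (d) requires chemistry at all 5 dose steps, whereas 6.3 and Appendix D's Medium row do not require it after the last three. A literal reading of 6.3 could cost three next-day checks per affected patient. How many such patients there will be is unknown; eligibility from CrCl 40 makes them possible. This is a safety wording error that should be corrected.

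The ascertainment point is secondary. The 2-of-5 against 5-of-5 coverage is a fact of the schedule, but its effect on observed TLS is of unknown size, and may be nil if non-debulked patients are mostly Medium with CrCl of 80 or more. It calls for a clear statement of how TLS is analysed, not for a change of monitoring in excused patients.

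**What to change.** 1. **Section 6.3:** require Days 16, 23 and 30 for High burden and for Medium burden with CrCl below 80.
2. **Appendix D:** amend the Medium row and footnote d to match note (d), replacing the undefined at-risk group with those same two categories. Since Appendix D presents the prescribing information's recommendations, a study-specific note beneath the table would serve.
3. **Section 9.7.2:** state that TLS is analysed descriptively, as 9.2 says, and is not modelled or compared by debulking response. Keep the overall rate through ramp-up as the headline, and tabulate events by dose step and monitoring schedule.

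Restricting a comparison by debulking response to Cycle 0 and the 20 and 50 mg steps would not rescue it. Debulking is measured on Days 15-28 of Cycle 0, after that cycle's treatment on Days 1-4, so patients would be grouped by a later outcome. The early steps are also sampled unequally (4 draws per step against 2).

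The cost is wording and one table, plus a few draws and visits only where 6.3 was being followed instead of note (d). Giving up a model for TLS loses little at the event counts expected.
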